In addition to the reporting procedure outlined in Section 7.4 of the main "umbrella" protocol, SAEs will also be reported to eFFECTOR Therapeutics for subjects enrolled in the zotatifin plus fulvestrant arm only using the provided CRFs within 24 hours of learning of their occurrence.

SAE reporting guidelines to other entities outlined in Section 7.4 of the main "umbrella" protocol should continue to be followed for both subjects enrolled in the treatment and SOC arms (see also Section D-7.13). Follow-up information is submitted in the same way as the original SAE Report within 24 hours of the treating site learning of the follow-up information. Each re-occurrence, complication, or progression of the original event should be reported as a

follow-up to that event regardless of when it occurs. The follow-up information should describe whether the event has resolved or continues, if and how it was treated, and whether the patient continued or withdrew from study participation.

D-6.3. Pregnancy

In addition to the reporting procedure outlined in Section 7.5 of the main "umbrella" protocol, pregnancy of a subject or a pregnancy as a result from a male subject on the zotatifin plus fulvestrant arm only must also be reported to eFFECTOR Therapeutics within 24 hours upon learning of its occurrence using the provided CRFs. The pregnancy should be followed up to determine outcome, including spontaneous or voluntary termination, details of the birth, and the presence or absence of any birth defects, congenital abnormalities, or maternal and/or newborn complications, and should be reported within 5 days of the conclusion of the pregnancy. For male subjects, consent to report information regarding these pregnancy outcomes should be obtained from the mother.

D-7. STUDY CALENDAR – Cohorts 2 & 3 (Fulvestrant ± Zotatifin)

Cohorts 2 & 3 Treatment Phase

Protocol Activity	Screening	Treatment		Surgery/Biopsy	Follow-Up
	Within 14 days of Day 1 of treatment	Day 1 ¹⁴	Day 8 (± 3 days)	Day 15 (-3, +6 days)	30 Days (+/-7 days) after Final Day of Treatment ¹⁵
Informed Consent ¹	X				
Medical/Oncologic History ²	X				
Physical Examination ³	X	X			
ECOG Performance Status ⁴	X				
Safety Labs/Measurements					
Vital Signs ⁵	X	X		X	
Blood Laboratory Tests ⁶					
• Complete Blood Count with Differential					
• Complete Metabolic Panel	X	X (for zotatifin arm only)			
• Creatine phosphokinase (CPK)					
• Calcium	X	X (for zotatifin arm only)	X (for zotatifin arm only)	X (for zotatifin arm only)	
• Prothrombin Time (PT)					
• Partial Thromboplastin Time (PTT)	X			X (for zotatifin arm only)	
• Magnesium					
• Serum pregnancy (WOCBP only)	X				
Electrocardiogram ⁷	X				
Registration ¹	X				
Treatment					

Fulvestrant Administration ⁸		X			
Zotatifin Administration ⁹		X			
Tumor Assessment					
Post-treatment Tumor Tissue ¹⁰				X	
Research Plasma Collection ¹¹				(X)	
Other Clinical Assessment					
Adverse Event Assessment ¹²	X	X	X (for zotatifin arm only)	X	X
Concomitant Medications ¹³	X	X	X (for zotatifin arm only)	X	X

Footnotes: See numbered sections below.

D-7.1. Informed Consent: Must be obtained prior to undergoing any study specific procedure and may occur prior to the 14-day screening period. Registration in OnCore should have already occurred after signed informed consent for the main "umbrella" protocol. Subject assignment to a treatment cohort will be entered in OnCore when eligibility is documented. If not yet done, the subject's surgery or core biopsy should also be scheduled. Last day of screening can be as late as C1D1.

D-7.2. Medical History: Includes but not limited to history of other diseases (active or resolved), concomitant illnesses, prior endocrine therapy usage, menopausal status and OncotypeDX results (if available). Prior endocrine therapy includes tamoxifen, raloxifene, anastrozole, letrozole, exemestane, fulvestrant, or other anti-estrogen therapy as determined by investigator; note that ovarian suppression agents (e.g. leuprolide, goserelin) do not count as prior endocrine therapy. Prior endocrine therapy could have been for treatment of a previous breast cancer, treatment of this breast cancer (for those with in-breast recurrences), for breast cancer risk reduction, or for other reason determined by investigator. The exception is usage of these agents for reproductive endocrinology or fertility purposes, which do not count as "prior endocrine therapy".

D-7.3. Physical Examination: Includes an examination of major body systems and weight. Height from within the last 2 years should be recorded. On the day of zotatifin administration day (C1D1), the dose amount should be prepared based on the patient's weight in kilograms.

D-7.4. ECOG Performance Status

Score Definition

- 0 Fully active, able to carry on all pre-disease activities without restriction
- 1 Restricted in physically strenuous activity but ambulatory and able to carry out work of a light or sedentary nature, eg, light house work or office work
- 2 Ambulatory and capable of all selfcare but unable to carry out any work activities. Up and about more than 50% of waking hours
- 3 Capable of only limited selfcare, confined to bed or chair more than 50% of waking hours
- 4 Completely disabled. Cannot carry on any selfcare. Totally confined to bed or chair
- 5 Dead

D-7.5. Vital Signs: Blood pressure, pulse rate, and body temperature to be recorded in the same position, either supine or sitting.

D-7.6. Blood Laboratory Tests: All subjects will have labs performed at screening, which includes complete blood count with differential, comprehensive metabolic panel, calcium, magnesium, and creatine phosphokinase (CPK).

Coagulation studies including PT and PTT will also be done at screening. For female subjects of childbearing potential, a serum pregnancy test must also be performed at screening. Subjects randomized to the zotatifin plus fulvestrant arm will have complete blood count with differential, comprehensive metabolic panel, calcium, and creatine phosphokinase checked on Day 1 prior to drug administration and again on Day 8. They will have complete blood count with differential, comprehensive metabolic panel, calcium, creatine phosphokinase, PT and PTT checked on the day of surgery or biopsy; and have complete blood count with differential, comprehensive metabolic panel at the 30-day follow-up. The Day 1 labs do not need to be repeated if the Screening labs were within 72 hours before start of study therapy.

D-7.7. Electrocardiogram: 12-lead ECG in triplicate to assess for exclusion criteria of significant screening ECG abnormalities. It is suggested that the three measurements be obtained within 1 hour.

D-7.8. Fulvestrant Administration: Fulvestrant will be administered on Day 1. A total of 500 mg Fulvestrant should be administered intramuscularly into the buttocks slowly (1 to 2 minutes per injection) as two 5 mL injections, 1 in each buttock. Instructions in the package insert should be followed for safety concerns.

D-7.9. Zotatifin Administration: Subjects will be administered zotatifin 0.10 mg/kg as a 60-minute IV infusion (a window of 50 minutes to 120 minutes is permitted, as needed) on Day 1. For the order of administration, fulvestrant should be given prior to zotatifin when possible.

D-7.10. Post-treatment Tumor Tissue: Subjects will either undergo core biopsy or definitive surgery on Day 15 (-2, +7 days). The collected tumor tissue will be sent to central laboratory, and Ki67 immunohistochemistry performed. For those participants who undergo surgery (not core biopsy), information from their surgical pathology report will also be collected as available, including but not limited to tumor size, T-stage, N-stage, and grade; T- and N-stage will be used to calculate the modified PEPI score centrally.

D-7.11. Research Plasma Collection: Research plasma collection for cell-free DNA/RNA and matched normal (if feasible), to be sent to central laboratory. The collection may occur (if feasible) on the day of surgery or core biopsy (or up to 2 days prior) and may be obtained at the same time as the blood laboratory tests for patients on the zotatifin arm. It is not a protocol deviation if this collection does not occur.

D-7.12. Adverse Event Assessment: Adverse events (AEs) will be documented and recorded using NCI CTCAE v5.0. For serious adverse events (SAEs), the active reporting period will be from the time that the subject provides informed consent, which is obtained prior to the subject's participation in the study, ie, prior to undergoing any study-related procedure and/or receiving investigational product, through and including 30 calendar days after the last administration of the investigational product. SAEs experienced by a subject after the active reporting period has ended should be reported if the Investigator becomes aware of them. The reporting period for non-serious AEs will be from the time the subject has taken at least one dose of study treatment throughout time on study. All events regardless of grade will be monitored until all drug-related toxicities have resolved or the Investigator determines in his/her clinical judgment that no further improvement is expected. Adverse events should be assessed at any scheduled or unscheduled visit.

D-7.13. Concomitant Medications: Concomitant medications will be recorded at screening. All concomitant medications should be recorded in the CRF including supportive care drugs (eg, anti-emetic treatment and prophylaxis), herbal supplements or vitamins, the drugs used to treat adverse events or chronic diseases, and non-drug supportive interventions (eg, transfusions).

D-7.14. Day 1 of Treatment: Day 1 of treatment should take place 14 days (-2, +7) before scheduled biopsy or surgery.

D-7.15. 30-Day Safety Follow-Up: To be performed 30 ± 7 days after last dose of study drug. Information related to concomitant medications and adverse events will be collected for 30 days after the last dose of the study drug, and the information may be obtained in person, by telephone or by e-mail contact.

D-8. STATISTICAL CONSIDERATIONS

D-8.1. Statistical Design

The primary objective of this study is to evaluate the efficacy of combination fulvestrant and zotatolifin compared with fulvestrant alone in reducing Ki67 values from baseline to on-treatment biopsy after 14 days of treatment in estrogen receptor-positive, HER2-negative tumors (tumor size ≥ 1 cm) with Ki67 $\geq 10\%$ that classify as integrative subtype 2 or 6 by integrative subtype screening.

Additional statistical considerations will follow the details provided in the main "umbrella" protocol.

Two exploratory analyses will be done. First, we will assess if there is a differential treatment effect by integrative subtype (IC2 vs IC6) by including an interaction term between treatment arm and integrative subtype in the main ANCOVA models. Second, we will pool the data from Cohorts 2 and 3 and fit the main ANCOVA models with two extra variables: a binary flag for cohort (cohort 2 vs. cohort 3) and an interaction between treatment arm and that flag. To avoid the risk of false discovery with multiple comparisons, we will not report p-values from these models, but only the point estimates and 95% CIs for the interaction terms.

D-8.2. Accrual Considerations

Each cohort of the study will need to accrue approximately 3 subjects per quarter to accrue the planned 50 subjects in 4 years for each cohort. Subjects will be recruited to participate in this study from an anticipated 10-15 sites, including Stanford Cancer Center. Similar sites have successfully completed accrual to TRIO 030 ([NCT03004534](#)), a window-of-opportunity study of an androgen receptor inhibitor in 36 early-stage breast cancer subjects. Early accrual to this study was predominantly patients with ER⁺/HER2⁻ breast cancer (the study also had a triple-negative breast cancer cohort), and during their first quarter, 7 patients were accrued to this study. As the study population in the present trial is anticipated to be 8% of the overall population of patients with ER⁺/HER2⁻ breast cancer, it will be necessary to screen approximately 40 patients per quarter to enroll 3 subjects. Thus, 6 sites performing similarly in the aforementioned window-of-opportunity trial would complete accrual on schedule, and it is anticipated that a total of 10-15 sites, recognizing that not all will have equivalent accrual capacity, should enable adequate accrual.

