The dose amount required to prepare the zotatifin infusion solution will be based on the patient's weight in kilograms (kg). All patients should be weighed on the day of dosing, prior to the infusion. If the patient experiences either a weight loss or gain > 10% compared to the weight used for the last dose calculation, the amount of zotatifin must be recalculated using the most recent weight obtained.

Refer to the Study Pharmacy Manual for complete instructions on zotatifin preparation.

Given the nausea and vomiting that has been observed at the 0.1mg/kg dose of zotatifin, premedication with ondansetron (for example, 16mg PO x1 or 8mg IV x1) prior to zotatifin administration is recommended, but not mandated.

D-4.1.7. Investigational Agent Compliance and Accountability

See Section 5.4 Investigational Agent Compliance and Accountability of the main protocol for information on compliance and accountability of zotatifin.

D-5. STUDY DRUG ADMINISTRATION

D-5.1. Dosing Regimen

D-5.1.1. Zotatifin (eFT226)

Subjects in the investigational arm should receive Zotatifin via IV once (e.g., on Day 1 of the 14-day treatment period) by 1-hour infusion at the study site. However, given the variability of infusion pumps from site to site and patient tolerability of the infusion, time windows of minus 10 minutes and plus 60 minutes are permitted (ie, infusion time is 50 to 120 minutes); infusion time may be extended beyond 120 minutes if needed to manage infusion-related reactions.

D-5.1.2. Fulvestrant

Subjects in the investigational or standard of care arm should receive fulvestrant once intramuscularly via injection on Day 1 (up to 3 days late is permissible).

D-5.2. Infusion-related Reactions

It is unknown if a patient will experience an infusion-related reaction (IRR) with the administration of zotatifin (eFT226). Currently, premedication for IRR is not part of the treatment regimen for zotatifin.

Signs and symptoms of IRRs may include, but are not limited to; fever; chills; pruritus; headache; nausea; chest pain; palpitations; edema; rash; tachycardia; bradycardia; hypotension; hypertension; rigors; and shortness of breath.

In the case of an IRR, the IND-holder and manufacturer should be notified.

Recommended management for IRRs is provided in Table D-2. Institutional standards for the treatment of IRRs may also be used. The recommended management does not supersede Investigator judgment.

Table D-2: Management of Zotatifin Infusion-Related Reactions

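### Counted from the last dose, the 30 ± 7 day safety contact can fall on day 23, before the 30-day adverse event and SAE collection period ends, and the calendar heading uses a different anchor

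*Combined protocol and SAP*

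**What the plan says.** All Appendix D references concern Cohorts 2 and 3 (fulvestrant with or without zotatifin).

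- **Timing of the contact, D-7.15:** "To be performed 30 ± 7 days after last dose of study drug".
- **Collection period, next sentence of D-7.15:** "Information related to concomitant medications and adverse events will be collected for 30 days after the last dose of the study drug". The information may be obtained in person, by telephone or by e-mail.
- **SAE period, D-7.12 and section 7.4:** "through and including 30 calendar days after the last administration of the investigational product". Section 7.5 also uses 30 days, counted from the last dose of study drug.
- **Non-serious events, D-7.12:** "The reporting period for non-serious AEs will be from the time the subject has taken at least one dose of study treatment throughout time on" (the trial), with no day number for the end.
- **D-7 calendar, follow-up column:** "30 Days (+/-7 days) after Final Day of Treatment". Its footnote 15 leads to D-7.15.
- **Dosing, D-5.1:** zotatifin is infused once, on Day 1. The schedule for the other drug is "fulvestrant once intramuscularly via injection on Day 1 (up to 3 days late is permissible").

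**The concern.** A visit tolerance normally lets a site book around the end of a data period without shortening it. Here the tolerance is symmetric around the day on which the collection period ends, so a contact on the early side comes before that end. A site can keep to the calendar, see the subject on day 23 and have no further scheduled occasion to ask about days 24 to 30. How completely late events are ascertained then depends on when the contact was booked.

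What is at stake is the completeness of the safety data. Appendix D says that the maximum tolerated dose of zotatifin is not yet defined, and that three DLT-evaluable participants had been enrolled at the fulvestrant-combination dose and schedule on which this study's dose is based. The DSMB reviews safety on an ongoing basis (section 11.2). The formal toxicity rule in section 12.2 acts on a small count: 4 of the first 12 patients with treatment-related SAEs of Grade 3 or higher.

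**Working it through.** This is day arithmetic; no sample size, power or alpha is involved.

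**Inputs.** Contact 30 ± 7 days after the last dose (D-7.15). Adverse event collection for 30 days after the last dose (D-7.15). SAE reporting through 30 days after the last investigational product (D-7.12, section 7.4). Zotatifin on Day 1 (D-5.1.1). Fulvestrant on Day 1 or up to 3 days later (D-5.1.2). Tissue on Day 15, with −2/+7 days in D-7.10 and −3/+6 days in the calendar heading.

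**1. The plan's own window.** Earliest contact 30 − 7 = day 23; latest 30 + 7 = day 37. For a Day 1 dose, study day = days after dose + 1. The window is therefore study Days 24 to 38, and the 30-day period ends on study Day 31.

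**2. Days without a scheduled enquiry.** For a contact d days after the last dose, the gap is max(0, 30 − d).

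| Contact, days after last dose | Gap (days) |
|---|---|
| 23 | 7 |
| 27 | 3 |
| 30 to 37 | 0 |

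**3. Does another scheduled contact cover days 24 to 30?** The previous one is surgery or biopsy. Its latest date is study Day 22 under D-7.10 (22 − 1 = 21 days after a Day 1 dose) or Day 21 under the calendar heading (20 days after). Neither reaches day 24. The calendar lists nothing after the safety follow-up, and no text asks for a second contact if the first is made before day 30.

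**4. Late fulvestrant.** Suppose fulvestrant is given L days late and counts as the last study drug. The earliest contact is then 23 + L days after zotatifin. The SAE gap, counted from zotatifin, is 30 − (23 + L) = 7 − L, that is 7, 6, 5 or 4 days for L = 0 to 3. The adverse event gap stays at 7, because D-7.15 counts contact and collection from the same dose.

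**5. The other anchor.** Suppose the final day of treatment in the calendar heading means the day before tissue collection on study Day b. The earliest contact is then on study Day (b − 1) + 23 = b + 22, which is b + 21 days after a Day 1 dose.

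| Tissue day b | Earliest contact, days after Day 1 dose | Gap to day 30 |
|---|---|---|
| 12 (calendar heading, earliest) | 33 | 0 |
| 13 (D-7.10, earliest) | 34 | 0 |
| 15 (nominal) | 36 | 0 |
| 22 (D-7.10, latest) | 43 | 0 |

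With collection still counted from the Day 1 dose, this anchor leaves no gap.

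**The case against.** **The anchor.** The synopsis has all treatment end on the day before surgery or biopsy, and Appendix D speaks of a 14-day treatment period. Read that way, the calendar heading removes the gap (step 5). This stands in part. Against it, the heading's own footnote is D-7.15, which counts from the last dose; section 4 states the day-before rule for oral drugs, and both drugs in Appendix D are given by injection or infusion. The text does not settle the matter. A reader might infer that the gap exists whichever anchor is used; the documents do not support that.

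**The standing duty.** D-7.15 itself requires collection for 30 days, so a site that stops asking on day 23 meets the visit window but not that sentence. This stands: the window is no licence to stop collecting. What is missing is the step by which collection is completed after an early contact.

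**Other capture.** Events are assessed at unscheduled visits, known Grade 3 or 4 events are monitored at least every 2 weeks (section 7.4), and later SAEs are reported if the investigator becomes aware of them. A reader might call 7/30 = 23% of the period unobserved; these routes make that too strong. But none of them is a scheduled enquiry about new events on days 24 to 30.

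**Small consequence.** Zotatifin is given once, with a half-life of about 4 days (D-1.2.1.4), so day 23 is 23/4 = 5.75 half-lives after the dose. The window is the same in both arms. Nothing in the documents shows that events on days 24 to 30 would change the section 12.2 rule. This stands and keeps the point minor.

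**Conclusion.** The point holds under the D-7.15 anchor. The last scheduled safety contact may precede the end of the collection period, leaving 0 to 7 of 30 days without a scheduled enquiry about new events. The size depends on the contact day, and a contact on days 30 to 37 leaves no gap. How often sites would book early is not stated, so no number of missed events can be given.

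A reader might also infer that most peri-operative events would be missed, because tissue on Day 22 and contact on Day 24 are only 2 days apart. That pairs two extreme dates. The nominal dates are Day 15 and Day 31 (30 days after a Day 1 dose), some subjects have only a core biopsy, and the documents give no distribution of event timing.

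The conclusion assumes that the D-7.15 wording governs over the calendar heading; if the heading governs in the sense of step 5, the gap disappears. In either case the two anchors conflict and need one answer. The issue is minor and confined to safety ascertainment. The Ki67 endpoint, power and error rates are unaffected.

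**What to change.** 1. Reconcile the calendar heading, D-7.15 and D-7.12 so that the safety contact and the collection period are counted from one named anchor.
2. State in D-7.15 that the final adverse event and SAE enquiry is made no earlier than the end of the stated 30-day collection period, including when the visit or blood tests take place earlier in the window.

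The blood tests need not move. D-7.6 places a blood count and metabolic panel at this follow-up in the zotatifin arm, so shifting the whole visit would cost more than wording. D-7.15 already accepts telephone or e-mail for the adverse event information, so that enquiry can be made separately.

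Cost: a wording amendment, plus either slightly less booking flexibility or one additional remote contact for subjects seen early. No dose or treatment rule changes.

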APPENDIX D-A: Eligibility Criteria Checklist Specific for Cohort 2 & 3 (Zotatifin)

I. Protocol Information:

Protocol Title:	An Umbrella, Randomized, Controlled, Pre-Operative Trial Testing Integrative Subtype-Targeted Therapeutics in Estrogen Receptor-Positive, HER2-Negative Breast Cancer
Cohort 2:	IC2 or IC6 (zotatifin and fulvestrant vs. fulvestrant only)
Cohort 3:	Typical Risk (zotatifin and fulvestrant vs. fulvestrant only)
Local Protocol Number (Stanford):	(Stanford BRS0124 / IRB-52869)
Local Institution:	
Local Principal Investigator:	

II. Participant Information:

Participant Name/ID:

III. Inclusion Criteria

Prospective Participant Must MATCH ALL these Inclusion Criteria to be Eligible	Yes	No	Supporting Documentation *
1. Biopsy-proven ER-positive, HER2-negative breast cancer. ER-positivity is defined as $\geq 1\%$ cells staining positive by immunohistochemistry. HER2-negativity is defined by IHC or FISH, per ASCO-CAP 2018 guidelines. Breast tumor must be intact and tumor size must be $\geq 1\text{ cm}$ as measured by ultrasound, mammogram, MRI, or clinical exam. If tumor is locally recurrent, it must be in the breast (not skin, node, or chest wall recurrence). In the pre-screening phase, Ki67 may or may not have been done locally. If done locally, Ki67 score must be $\geq 5\%$. Any nodal status is allowed, as is M0 or M1 disease.			
2.  Cohort 2: Integrative subtype tumor classification as integrative subtype 2 (IC2, N = 25) or as integrative subtype 6 (IC6, N = 25) per [name] laboratory.  Cohort 3: Integrative subtype tumor classification as Typical Risk (N = 50) per [name] laboratory.			
3. Breast tumor Ki67 score $\geq 10\%$ as assessed by central laboratory.			
4. Women or men, age ≥ 18 years old.			

Prospective Participant Must MATCH ALL these Inclusion Criteria to be Eligible	Yes	No	Supporting Documentation *
5. Performance status 0 to 1 (by Eastern Cooperative Oncology Group [ECOG] scale).			
6. Ability to understand and the willingness to sign a written informed consent document.			
7. Adequate bone marrow and organ function, defined as: 
 
3.1. Absolute neutrophil count $\geq 1.5 \times 10^9/L$ 
3.2. Platelets $\geq 100 \times 10^9/L$ 
3.3. Hemoglobin $\geq 9.0 \text{ g/dL}$. 			
8. Adequate hepatic function during Screening as defined as: 
 
4.1. Serum alanine aminotransferase (ALT) $\leq 3 \times$ upper limit of normal (ULN) 
4.2. Serum aspartate aminotransferase (AST) $\leq 3 \times$ ULN 
4.3. Serum bilirubin $\leq 1.5 \times$ ULN (unless due to Gilbert's syndrome or hemolysis, in which case $\leq 3 \times$ ULN is permitted) 			
9. Adequate kidney function during Screening as defined as measured or estimated creatinine clearance (eCl _{CR}) $> 50 \text{ mL/min}$ (eCl _{CR} to be calculated by the Cockcroft-Gault formula)			
10. Adequate electrolyte values within 72 hours before the start of study therapy: 
 
6.1. Serum potassium within normal limits (WNL) 
6.2. Serum calcium (adjusted for serum albumin concentration) WNL 
6.3. Serum magnesium WNL 
Note: Oral or IV supplementation or medical therapy may be used to achieve normal values for serum potassium, calcium, and magnesium.
 
Patients with abnormal serum chemistry values may still be considered for the trial if there is adequate assessment and documentation from the Principal Investigator that the patient is asymptomatic, and the values are not clinically significant. Patients who show clinical signs and symptoms related to their abnormal serum chemistry values as well as patients whose serum chemistry values are asymptomatic but clinically significant (eg, hypokalemia or hyponatremia) should be excluded.
			

Prospective Participant Must MATCH ALL these Inclusion Criteria to be Eligible	Yes	No	Supporting Documentation *
11. Adequate coagulation profile: 7.1. Prothrombin time (PT) $\leq 1.5 \times$ ULN (Grade ≤ 1) Note: Does not apply if patient is stable and on therapeutic doses of an approved anticoagulant for deep vein thrombosis (DVT) or pulmonary embolism PE). 7.2. Activated partial thromboplastin time $\leq 1.5 \times$ ULN (Grade ≤ 1)			
12. Creatine phosphokinase (CPK) $\leq 1.5 \times$ ULN			
13. For female patients of childbearing potential, a negative serum pregnancy test within 7 days prior to start of study therapy.			
14. For female patients of childbearing potential, documented willingness to use a protocol-recommended method of contraception from the start of the screening period until ≥ 30 days after the final dose of study therapy. Note: A female patient is considered to be of childbearing potential unless she has had a hysterectomy, bilateral tubal ligation, or bilateral oophorectomy; has medically documented ovarian failure (with serum estradiol and follicle-stimulating hormone [FSH] levels within the institutional laboratory postmenopausal range and a negative serum or urine beta human chorionic gonadotropin [βHCG]); or is menopausal (age ≥ 55 years with amenorrhea for ≥ 6 months).			
15. For male patients who can father a child and are having intercourse with females of childbearing potential who are not using adequate contraception, documented willingness to use a protocol-recommended method of contraception from the start of study therapy until ≥ 30 days after the final dose of study therapy and to refrain from sperm donation from the start of study therapy until ≥ 90 days after administration of the final dose of study therapy. Note: A male patient is considered able to father a child unless he has had a bilateral vasectomy with documented aspermia or a bilateral orchiectomy.			

IV. Exclusion Criteria:

Prospective Participant Must NOT MATCH ANY these Exclusion Criteria	Yes	No	Supporting Documentation *
1. Significant cardiovascular disease (eg, myocardial infarction, arterial thromboembolism, cerebrovascular thromboembolism) within 6 months prior to start of study therapy; symptomatic dysrhythmias or unstable dysrhythmias requiring medical therapy; unstable angina; symptomatic peripheral vascular disease; New York Heart Association Class 3 or 4 congestive heart failure; uncontrolled Grade \geq 3 hypertension (diastolic blood pressure \geq 100 mmHg or systolic blood pressure \geq 160 mmHg) despite antihypertensive therapy; or history of congenital prolonged QT syndrome			
2. Significant screening ECG abnormalities, including unstable cardiac arrhythmia requiring medication, left bundle-branch block, 2 nd degree atrioventricular (AV) block type II, 3 rd degree AV block, Grade \geq 2 bradycardia, or corrected QT (QTcF) $>$ 450 msec (based on the average of 3 measurements at 5-minute intervals).			
3. Evidence of an ongoing systemic bacterial, fungal, or viral infection (including upper respiratory tract infections) at the time of start of study therapy. Note: Patients with localized fungal infections of skin or nails are eligible.			
4. Known active hepatitis B virus (HBV), hepatitis C virus (HCV), human immunodeficiency virus (HIV), or acquired immunodeficiency syndrome-related illness. Note: Patients with treated and inactive HBV, HCV, or HIV may enroll, following discussion with the Sponsor.			
5. Major surgery within 4 weeks before the start of study therapy or not fully recovered from major surgery.			
6. Prior solid organ transplantation.			

Prospective Participant Must NOT MATCH ANY these Exclusion Criteria	Yes	No	Supporting Documentation *
7. Ongoing immunosuppressive therapy, including systemic or enteric corticosteroids. Note: At screening, patients may be using systemic corticosteroids (at doses of ≤ 10 mg of prednisone or equivalent) or topical or inhaled corticosteroids. During study therapy, patients may use systemic, enteric, topical or enteric corticosteroids as required for treatment-emergent conditions.			
8. Use of a strong or moderate inhibitor or inducer of cytochrome P450 (CYP) 3A4 within 7 days prior to the start of study therapy or expected requirement for use of a strong or moderate inhibitor or inducer of CYP3A4 during study therapy.			
9. See Appendix D-B for a list of prohibited concomitant medications and supplements	N/A	N/A	N/A
10. Any other concurrent severe and/or uncontrolled medical condition that would, in the investigator's judgment, contraindicate subject participation in the clinical study (eg, chronic active hepatitis [testing not mandatory unless required by local regulations or requirements], severe hepatic impairment, etc)			If Yes, ineligible by investigator decision.
11. Pregnant or nursing (lactating)			
12. Prior breast cancer-directed therapy (surgery, radiation, chemotherapy, or endocrine therapy to treat breast cancer) is not allowed, with the exception of people with in-breast recurrences. People with in-breast recurrences cannot have had breast cancer-directed therapy (radiation, chemotherapy, or endocrine therapy; surgery is acceptable) within the 6 months prior to signing the pre-screening consent. Previous endocrine therapy for breast cancer risk reduction and/or ovarian suppression for premenopausal women is allowed.			

* All participant files must include supporting documentation to confirm participant eligibility. The method of confirmation can include, but is not limited to, laboratory test results, radiology test results, participant self-report, and medical record review.

VI. Statement of Eligibility

By signing this form of this trial I verify that this participant is [**eligible** / **ineligible**] for participation in the study. This study is approved by the Stanford Cancer Institute Scientific Review Committee, the study's IRB of record, and has finalized financial and contractual agreements as required by Stanford School of Medicine's Research Management Group.

Site PI or Treating Physician Signature:	Date:
Printed Name:	

Secondary Reviewer Signature:	Date:
Printed Name:	

Study Coordinator Signature:	Date:
Printed Name:	

